## 1.0 INTRODUCTION

### 1.1 Introduction

The overall goal of this study will be to determine whether NAC will help to support dopaminergic function in patients with Parkinson's disease (PD). This SPECT study will utilize Ioflupane (DaTscan) single photon emission computed tomography to measure dopamine function, magnetic resonance spectroscopy (MRS) to measure inflammatory and oxidative stress markers, and neurological measures to assess clinical symptoms, in patients with PD who are given oral and IV infusions of NAC which is thought to support the dopamine system's function.

Parkinson's disease (PD) is a devastating neurodegenerative disorder of unknown cause that affects more than a million Americans (Korell and Tanner, 2005). Its cardinal features include tremor, rigidity, bradykinesia, and postural instability. Depression is common, and a fourth to a half of all PD patients eventually develop dementia (Shulman et al., 2005). The most prominent PD pathology is degeneration of dopaminergic neurons in the ventrolateral tier of the pars compacta of the substantia nigra in the midbrain, and the formation of  $\alpha$ -synuclein cytoplasmic inclusions, termed Lewy bodies, throughout the brain (Fearnley and Lees, 1991). Unfortunately, by the time of clinical diagnosis, substantial neural damage has been wrought, with an 80% reduction in striatal dopamine and a 60-70% reduction of the neurons in the substantia nigra (Bernheimer et al., 2005). It is believed that oxidative stress and inflammation play an important role in the pathophysiology of PD.

The purpose of this study is to evaluate whether NAC that has been shown to have either anti-inflammatory or anti-oxidant effects that might support brain function in patients with PD, particularly with regard to the dopamine system. One arm of this study will receive intravenous and oral NAC, which is a strong antioxidant that increases brain glutathione, that may be beneficial in PD. The second arm will be a waitlist control receiving standard PD therapy. It should be noted that both arms will receive standard PD therapy. One arm will be augmented with the NAC. Since we are not seeking specifically to determine the use of NAC as a treatment for PD, an IND is not required based upon current FDA guidelines.

### 1.2 Oxidative Stress in PD

A number of studies have suggested the importance of oxidative stress in the pathophysiology of PD. Oxidative stress itself is classically defined as a redox imbalance in which there is an excess formation of oxidants or a decrease in amount of function of antioxidants (1). The brain has difficulty withstanding substantial amounts of oxidative stress because of the presence of high amounts of polyunsaturated fatty acids, low levels of antioxidants such as glutathione, and increased iron content in specific areas such as the globus pallidus and the substantia nigra (SN) (2). Finally, since neurons are in a post-mitotic state, they are unlikely to recover from an oxidative stress insult.

The mechanism by which oxidative stress occurs begins with the production of reactive oxygen species such as superoxide anion ( $O_2^-$ ), hydrogen peroxide ( $H_2O_2$ ) and hydroxyl radical

(UOH), which are byproducts of metabolism of molecular oxygen by the mitochondria. Excessive formation of reactive oxygen and nitrogen species in PD may damage key cellular components such as lipids, proteins, and DNA. Reactive nitrogen species such as nitric oxide (NO) and its metabolite peroxy nitrite (PN) may also play a major role in PD. The “free radical hypothesis” has become prominent in attempting to explain the etiology of PD (3). Evidence for oxidative damage in the brain of PD patients includes the finding of an increase in the amount of lipid peroxidation products such as malondialdehyde and 4-hydroxynonenal, an increase in protein oxidation as evidenced by protein cross-linking and fragmentation, and an increase in the concentration of 8-hydroxy-2'-deoxyguanosine, a product of DNA oxidation (2).

Additional evidence suggests that reactive oxygen species (ROS) that are derived from the combined presence of dopamine itself, low glutathione, and high iron concentrations are a major cause of dopaminergic cell loss in the brains of PD patients (4,5). Dopamine is chemically unstable and undergoes auto-oxidation to form dopamine quinones (DAQs) and superoxide anion radicals. This reaction is catalyzed by the presence of metals, oxygen, and enzymes such as tyrosinase. The DAQs can further act as oxidants thus supporting ROS formation. Auto-oxidation of dopamine may be increased in the early stages of PD when dopamine turnover is increased to compensate for dying dopaminergic neurons (6).

Glutathione is an important reducing agent in the neurons, which is found to be depleted in the brain of PD patients. Glutathione depletion may result from an accelerated loss of glutathione or diminished production. Glutathione is not the only antioxidant molecule reported to be altered in PD, but the magnitude of glutathione depletion appears to parallel the severity of the disease and is the earliest known indicator of nigral degeneration, apparently preceding detectable losses in striatal dopamine (7,8).

Glial cells may also contribute to the problem of oxidative stress in PD even though such cells are protected from toxic levels of H2O2 by possessing high levels of glutathione and glutathione peroxidase that act to detoxify H2O2 to water. However, dopamine is metabolized into H2O2 in glial cells by monoamine oxidases (MAOs). The MAO-B isoform is particularly abundant in the substantia nigra and since the H2O2 produced in glial cells by MAO-B is highly membrane-permeable, H2O2 can cross into neighboring dopaminergic cells. In the dopaminergic cells, H2O2 can react with free iron (Fe++) to produce the hydroxyl radical, which can damage cellular components.

Iron content in the substantia nigra has been found to be elevated in PD compared to age-matched controls. Increased levels of iron and Fe (II) enhance the conversion of H2O2 to the hydroxyl radical via the Fenton reaction. Furthermore, oxidative stress may enhance the levels of free iron via, for example, enhanced release of iron from ferritin by O2. It is not clear whether iron accumulation in the substantia nigra in PD patients is an early or late event and/or whether increased iron helps cause the neurodegenerative process or is a consequence of the pathological process. However, several lines of evidence suggest that iron accumulation along with subsequent oxidative stress may be a primary event in the degenerative process (9). For example, a number of iron chelators have been shown to attenuate MPTP toxicity suggesting that iron either mediates or accentuates the associated neuropathological events (10,11). Another study in mice showed that administration of a metal chelator, clioquinol (CQ), in dopaminergic midbrain

neurons protected them from MPTP mediated neurodegeneration (12). This also resulted in attenuation of motor deficits associated with MPTP in the chelator treated mice.

An additional component to the relationship between oxidative stress and PD is related to alpha-synuclein, a prominent component of Lewy body aggregates (13) which are a pathological hallmark of PD. Previous studies have implicated the role of increased oxidative stress in the formation of synuclein aggregates (14,15). Conjugation of dopamine with  $\alpha$ -synuclein impedes the usual transition from protofibril to fiber resulting in accumulation of more cytotoxic protofibrils in dopaminergic neurons. In addition, several studies have suggested that iron-related oxidative stress can promote  $\alpha$ -synuclein aggregation (16,17). Furthermore, soluble nitrated  $\alpha$ -synuclein, which results from interactions with oxidized nitrogen species, appears to activate microglia to produce substantial amounts of ROS through modulation of specific ion channels (18).

Overall, there appears to be substantial evidence that oxidative stress, and associated nitrosative stress, likely play a prominent role in the pathophysiology of PD. The normal homeostasis health of a neuron requires adequate maintenance of the redox potential in the cell. When oxidative stress occurs, the cell can no longer protect itself resulting in dysfunction and ultimately cell death. The question is whether interventions designed to restore the redox potential will be effective in attenuating the disease process.

### 1.3 Use of N-acetyl cysteine in PD Patients

NAC is the N-acetyl derivative of the naturally occurring amino acid, L-cysteine. It is a common over-the-counter supplement and also is available as an injectable pharmaceutical that protects the liver in cases of acetaminophen overdose. In the exercise physiology literature, both oral and injectable NAC have been shown to reduce fatigue and improve recovery from exertion (19,20), which has interesting implications for exploring fatigue related to PD.

Laboratory studies have suggested how NAC might have a beneficial effect in neurodegenerative disorders such as PD. For example, one study showed that NAC may reduce misfolded protein levels and ameliorate proteotoxicity through heat shock proteins (21). The authors suggested that their findings broaden the potential mechanisms of action for NAC in neurodegenerative proteinopathies. Another study tested the hypotheses that a combined exposure of nerve cells to oxidative stress caused by hydrogen peroxide and paraquat would elicit synergistic neurodegeneration and that this toxicity would be prevented by NAC (22). The findings revealed that when neuronal N2a cells received two hits of hydrogen peroxide the result was a severe loss of glutathione which was attenuated by NAC. In fact, NAC reduced the near-complete loss of cells after exposure to dual hydrogen peroxide hits.

NAC can prevent oxidative damage, telomere shortening, and cell death in an in vitro model that disrupts mitochondrial electron transport function. Thus, NAC could act in vivo against programmed cell death in PD (23). Long-term treatment with NAC alters NF-kappaB signaling in the brain of mice by increasing cytoplasmic retention of NF-kappaB. This prevents the action of NF-kappaB as a transcription factor in the nucleus (24) Since increased activation of NF-

$\kappa$ B may contribute to the pathology in models of Parkinson's disease, it is possible that the modulating effect of NAC on NF- $\kappa$ B activity may be another mechanism by which NAC helps patients with PD (25,26).

Another interesting study showed that NAC is a potent scavenger of both H2O2 and toxic quinones that are derived from dopamine which can contribute to cell death in PD. NAC also prevented dopamine-mediated inhibition of Na+, K+-ATPase activity suggesting another mechanism for the use of NAC in the treatment of PD (27). If NAC prevents Na+, K+-ATPase inhibition, it might counteract intracellular damage that leads to dopaminergic neuron death. A study of rat neurons found that NAC reduced methamphetamine induced neurotoxicity in dopaminergic neuronal cells (N27 cells) (28). Thus, NAC prevents the methamphetamine induced mitochondrial dysfunction and enhanced oxidative stress that induces apoptotic cell death as well as oxidative stress markers.

In animal studies, the administration of NAC has been shown to increase glutathione levels in the mouse brain (29,30). NAC also has been shown to reduce markers of oxidative damage (31), increase mitochondrial Complex I activity in nerve cells (32), and protect against dopamine cell death from MPTP toxicity (33,34,35).

In a mouse study, oral NAC was observed to protect dopaminergic terminals against loss related to over-expression of  $\alpha$ -synuclein (36). In  $\alpha$ -synuclein over-expressing mice, NAC administration was associated with increased striatal tyrosine hydroxylase positive terminal density and a decrease in  $\alpha$ -synuclein immuno-labeling. In addition, NAC administration significantly increased glutathione concentrations in the substantia nigra of mice over-expressing  $\alpha$ -synuclein.

A study of EAAC1(-/-) mice (these animals have neurons with impaired neuronal cysteine uptake, resulting in reduced neuronal glutathione content and chronic oxidative stress), showed substantially reduced neuronal loss when treated with NAC (37). The authors suggested that their approach may be a useful model for the chronic neuronal oxidative stress that occurs in PD and that the beneficial effects of NAC might provide an impetus for clinical evaluation of glutathione repletion in PD.

Finally, in humans, an MRS study of 3 patients with PD showed that Blood glutathione increased after the start of an NAC infusion and reached a maximum at approximately 60 to 75 minutes (38). Brain glutathione also increased with maximal values observed at approximately 90 to 110 minutes. Subjects who had the greatest percent change in blood glutathione after NAC infusion also had the greatest percent change in brain glutathione. The mean maximal percent change from baseline in brain glutathione was 55% in the PD patients and this was higher than the mean increase in patients with Gaucher's disease or healthy controls. Interestingly, none of the subjects returned to their baseline brain glutathione levels even at 120 minutes after NAC infusion. The results suggest that NAC might be useful in preventing oxidative damage in PD patients.

This also builds on a related study that investigated the possible direct benefit of intravenous glutathione using a randomized double blind placebo controlled study by Hauser et al (39) of 21 PD patients. The patients with PD had motor symptoms that were not adequately controlled on

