## **3.0 STUDY PLAN**

### **3.1 Subject Recruitment**

[figure not shown]
Subjects may be pre-screened by telephone using a standardized script and screening form. Verbal consent and HIPAA Authorization to obtain the prescreening information will be obtained from subjects prior to the prescreening interview. If subjects are prescreened in person, a signed consent and HIPAA Authorization to obtain prescreening information will be obtained. Information collected during pre-screening will be incorporated into the research records as source documentation for subjects included in the study. If subjects are not eligible to participate in the study they will be asked if the information provided in during prescreening maybe retained for consideration in other studies. Prescreening information will be retained for an indefinite period on an official screening form that will be kept in a secure locked area that will only be used by persons involved with research with this research Study.

We plan on recruiting up to 65 subjects over 3 years with the goal of recruiting 28 subjects who will receive approximately 90 days of combined intravenous/oral NAC, and then 14 subjects who will be in the waitlist control group receiving standard of care to be evaluated initially and then approximately 90 days later. This will allow for an attrition rate of up to one third. At the conclusion of the study, those in the waitlist control group will be given the option to receive a trial of oral/intravenous NAC if the data suggests that NAC is effective. All of the study subjects must be clinically diagnosed with PD by a referring neurologist. Subjects may be assessed using

structured examinations (i.e., the Unified Parkinson's Disease Rating Scale (UPDRS) or Movement Disorder Society (MDS) Unified Parkinson's Disease Rating Scale (MDS-UPDRS) and/or the Hoehn and Yahr scale. Diagnostic criteria will be applied using structured questionnaires, clinical interviews, and neurological examinations. Additional information is gathered, whenever possible, from family members, caregivers, review of previous medical records, and physical and laboratory examination. Subjects may take PD medications, but must be on a stable dose for at least 1 month prior to entering into the study.

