### 3.1.1 Flow Chart

### **3.1.2 Inclusion criteria**

1. Clinical diagnosis of PD
2. Age 30-80 years old
3. Physically independent, ambulatory
4. Hoehn and Yahr score of I-III inclusive.
5. On stable antiparkinsonian medication for at least one month
6. Women of childbearing potential will confirm a negative pregnancy test and must practice effective contraception during the period of pilot study. In addition, male subjects who have a partner of childbearing age should practice effective contraception.

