### **3.1.3 Exclusion criteria**

1. Known allergy to iodine, cobalt, or NAC that will be given in the study.
2. Previous brain surgery.
3. Score on Mini-Mental Status examination of 25 or lower.
4. Wheelchair-bound or bed-ridden, non-ambulatory.
5. Intracranial abnormalities that may complicate interpretation of the brain scans (e.g., stroke, tumor, vascular abnormality affecting the target area).
6. History of head trauma with loss of consciousness > 48 hours.
7. Any medical disorder or physical condition that could reasonably be expected to interfere with the assessment of parkinsonian syndrome symptoms, or with any of the study assessments including the SPECT imaging.
8. Patients with evidence of a significant psychiatric disorder by history/examination that would prevent completion of the study will not be allowed to participate.
9. Patients with current alcohol or drug abuse
10. Pregnant or lactating women.
11. Enrollment in active clinical trial/ experimental therapy within the prior 30 days.
12. Pending surgery during the course of the study.
13. History of very low blood pressure.
14. History of thrombocytopenia or clotting disorders.
15. Cancer patients receiving active chemotherapy.
16. History of active gallstone problems or a bile duct obstruction.
17. Severe gastroesophageal reflux disease.
18. History of uncontrolled diabetes, asthma, gastroesophageal reflux disease, thyroid conditions.
19. History of severe kidney disease (if a patient reports this problem, a serum creatinine will be checked to assess GFR and if it is less than 30, they will be excluded),
20. History of Leber's disease, a hereditary eye disease.
21. History of uncontrolled hypercalcemia
22. History of active sarcoidosis, histoplasmosis, or lymphoma.

23. Patients taking medications that might interact with NAC involved in this study will be evaluated on a case by case basis by the PI or study physician. These medications include: Medications for high blood pressure; Medications that slow blood clotting; Medications for diabetes; Nitroglycerin.

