## 4.0 RISKS

**4.1 N-acetyl cysteine:** Oral NAC has few side-effects and is commonly used as an over-the-counter supplement worldwide. Oral NAC has good, but variable absorption from the gut (69,70), making it problematic as the sole mode of supplementation in a clinical study. Injectable NAC is used at lower doses for exercise fatigue and higher doses primarily as a liver protector. The dosages in this study are consistent with those used in the exercise physiology literature (71). Side effects increase with higher dosage, and the most common associated adverse reactions in the literature attributed to IV NAC administration are rash, urticaria, and pruritus. The frequency of adverse events has been reported to be between 0.2% and 20.8%, and they most commonly occur during the initial loading dose of acetylcysteine at dosages higher than what will be used in this study. Other side effects with greater than 1% occurrence include nausea and bronchospasm, again at higher dosages. A hypersensitivity reaction to NAC has been reported as a rare occurrence. NAC should be used with caution in patients with asthma. Please note that the oral and intravenous NAC dose used in this study is the same as one we have used in a study of NAC in women with breast cancer. We have found the NAC to be generally well tolerated at the doses we will be using in the current study.

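### Non-study NAC, sold over the counter, is neither excluded at entry, restricted on the waitlist nor recorded on study, so the between-arm difference in 90-day change can be diluted by an unknown amount

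*Combined protocol and SAP*

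**What the plan says.** The plan describes the study agent as freely obtainable. Section 1.3 says "It is a common over-the-counter supplement", and section 4.1 says "Oral NAC has few side-effects and is commonly used as an over-the-counter supplement worldwide". The oral study product in 3.3.2 is itself a 600 mg capsule from a supplement supplier.

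The eligibility criteria that come nearest to outside NAC use are these:

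- Exclusion 1 concerns allergy: "Known allergy to iodine, cobalt, or NAC that will be given in the study".
- Exclusion 11 reads "Enrollment in active clinical trial/ experimental therapy within the prior 30 days". It does not name self-bought supplements.
- Exclusion 23 is a safety review: "Patients taking medications that might interact with NAC involved in this study will be evaluated on a case by case basis". It lists four drug classes, and so does 4.2.1; neither list includes NAC or glutathione.
- Inclusion 5 asks for stability of Parkinson's drugs only: "On stable antiparkinsonian medication for at least one month".

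Sections 1.1, 3.1 and 3.3.1 define the waitlist arm as standard Parkinson's care, with no instruction about supplements. No placebo is described, so controls know their assignment. Section 3.1 says that at the end of the study "those in the waitlist control group will be given the option to receive a trial of oral/intravenous NAC", on condition that the data suggest it works. Section 3.6.2 lists the case report forms and includes baseline history, but no record of supplements during follow-up. Section 3.8 does not say how outside NAC use would be handled.

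**The concern.** The trial contrasts 90-day change with NAC against 90-day change without it. Followed as written, the protocol admits people who already take NAC and lets controls begin it.

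If NAC has an effect, two groups distort the contrast. Controls who start NAC after baseline gain some of the effect in the arm meant to lack it. NAC-arm subjects already taking NAC start from a partly treated baseline and have less room to change. Both push the estimated difference towards zero on DAT binding, spectroscopic glutathione and clinical scores.

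Section 3.8.4 presents the trial mainly as a pilot that will supply an effect size for larger studies, so a diluted estimate would be carried forward. If on-study use is not recorded, the extent of dilution cannot be judged afterwards.

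**Working it through.** **Inputs.** From 3.8.4: about 28 NAC and 14 control subjects, DVR variability of about 10%, expected improvement of 5–10%, 80% power, p = 0.05, calculation based on simple t-tests. Assumed here: a two-sided test, and the 10% read as the SD of the quantity compared, because the plan states neither. The rate of outside NAC use and its effectiveness are not in the documents and are varied.

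**The plan's own figure.** For 2:1 allocation by the normal approximation, the control-arm size is (1.960 + 0.842)² × 10² × (1 + 1/2) / δ².

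- δ = 10%: 11.8, so 12 + 24 = 36.
- δ = 7.5%: 20.9, so 21 + 42 = 63.
- δ = 5%: 47.1, so 48 + 96 = 144.

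Neither end of the range, nor its midpoint, returns 14 + 28. That size has 80% power at δ = 2.802 × 10 × √(1/28 + 1/14) = 2.802 × 3.273 = 9.2%. The mismatch is a separate matter, and the present point does not depend on it.

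**Dilution of the contrast.** Let c be the share of controls who start NAC after baseline, b the share of the NAC arm already on it at baseline, and e the effect of outside NAC relative to study NAC.

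- Mean NAC effect on change, NAC arm: δ[(1 − b) + b(1 − e)] = δ(1 − eb).
- Mean NAC effect on change, control arm: δec. A control on a constant dose throughout contributes about zero, because baseline and follow-up are both treated.
- Difference: δ(1 − e(b + c)).

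**Power.** The noncentral t has 28 + 14 − 2 = 40 degrees of freedom, critical value 2.021 and noncentrality equal to the diluted difference divided by 3.273. For δ = 10% and b = 0:

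| Controls starting NAC | Full effect (e = 1): difference, power | Half effect (e = 0.5): difference, power |
|---|---|---|
| 0% | 10.0, 84.6% | 10.0, 84.6% |
| 5% | 9.5, 80.8% | 9.75, 82.8% |
| 10% | 9.0, 76.5% | 9.5, 80.8% |
| 20% | 8.0, 66.5% | 9.0, 76.5% |

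Two of 14 controls is 14%, which gives 72% power at full effect and 79% at half effect.

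**Check by simulation.** Drawing users at random adds some variance, which the formula ignores. At full effect and δ = 10%, simulated power is 84% with no outside use and 75% with 10% of controls starting. It is 64% when a further 10% of the NAC arm were already users (66.5% by the formula, with b + c = 20%).

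**Low end of the range.** At δ = 5%, power is 32% with no outside use and 27% with 10% of controls starting at full effect.

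**The estimate itself.** At e = 1 and b + c = 10%, the expected estimate is 90% of the true effect. A later trial sized on it would be larger than needed by 1/0.9² = 1.23; at 20%, by 1/0.8² = 1.56.

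**The case against.** The strongest objections concern size and mechanism.

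- **No rate is given, and outside NAC may be weaker.** Self-use would be oral only, whereas the study arm also receives weekly infusions. Section 4.1 calls oral absorption variable and problematic as the only route, and the human brain glutathione evidence in 1.3 comes from infusion. This stands. The full-effect column is an upper bound, and even the half-effect column is an assumption.
- **Not every control user dilutes the contrast.** A reader might infer that any control taking NAC lowers power as tabulated. The endpoint is 90-day change, so the table applies only to controls who start after baseline.
- **Sample size dominates at a 5% effect.** This also stands: power there is about 32% before any outside use.
- **Some prior use may surface anyway.** Sections 3.3.1, 3.6.2 and 4.2.1 provide for a history and a medication review at entry. These neither bar prior use nor cover follow-up.
- **A restriction may exist elsewhere.** The flow chart and consent pages are not available to this review. A participant instruction there cannot be ruled out, but it would not add the missing eligibility criterion.
- **Motive is uncertain.** A reader might infer that controls will seek NAC out. Section 3.3.1 says only that subjects hear of limited data, risks and benefits. The deferred offer in 3.1 could raise or lower the temptation; the documents do not say.

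**Conclusion.** The omission is real and its direction is clear: if NAC works, outside use by post-baseline starters in the control arm and by prior users in the NAC arm biases the difference in change towards zero.

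Its size is unknown. The illustration rests on a true difference at the top of the plan's range, an SD of 10%, a two-sided t-test and assumed rates of use. On those terms, 10% of controls starting NAC costs about 4 percentage points of power at half effect (84.6% to 80.8%) and about 8 at full effect (84.6% to 76.5%).

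The documents do not support a claim that the trial will lose a given amount of power, or that contamination is likely. Nor do they support reading the 30 days in exclusion 11 as a NAC washout, since that criterion concerns other trials and experimental therapy. The point is a cheap improvement that protects the planned contrast, not an error in a stated figure.

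**What to change.** - In 3.1.3, add an exclusion for current or recent use of non-study NAC or glutathione supplements. The sponsor should set and justify the look-back window; the documents contain no figure for it.
- In 3.3.1, state that subjects in both arms agree not to start non-study NAC or glutathione before the 90-day assessments are complete.
- In 3.6.2, add a supplement-use question at the baseline and 90-day visits in both arms.
- In 3.8, keep all randomised subjects in the main analysis whatever their supplement use. Any analysis without self-users should be labelled supportive only: it is a post-randomisation exclusion and can introduce bias, particularly with 14 controls.

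The cost is amendment wording and one question at two existing visits. The downside is that a few candidates would be excluded or delayed.
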